EPIDEMIOLOGY STUDY PROTOCOL

EFFECTIVENESS OF MINIMISATION MEASURES OF RISK MANAGEMENT PLAN (RMP): EDUCATIONAL MATERIALS

TITLE: Behaviour and knowledge survey regarding the educational materials provided to the Healthcare Professional population prescribing Aubagio® (cross-sectional survey)

Study type: Knowledge survey

Company: Sanofi

Version Number/Status: 1.1

Study number: Using the ClubNet numbering system

This study will be conducted in accordance with Sanofi standard operating procedures for GPE epidemiologic studies

Date: 8 May 2017 Total number of pages 25

PASS information:

Title:	Behaviour and knowledge survey regarding the educational materials provided to the Healthcare Professional population prescribing Aubagio® (cross-sectional survey)	
Protocol version	1.1	
identifier		
Date of last version of	February 27, 2017.	
protocol	•	
EU PAS register	n.a.	
number (if applicable)		
Active substance	Teriflunomide	
Medicinal product	Aubagio®	
Product reference	EU/1/13/838/001-005	
Procedure number	EMEA/H/C/002514/	
Marketing	Sanofi-Aventis Group, Paris, France	
authorization holder(s)		
Joint PASS	No	
Research questions	The objective of the survey is to assess descriptively knowledge and	
and objective(s):	behaviour of healthcare professionals who prescribe Aubagio about the items of the educational materials ('Healthcare Professional Education/Discussion Guide') and thus the effectiveness of these materials to promote safe and adequate use of Aubagio. Research questions: • What is the knowledge of healthcare professionals about the healthcare professionals Education/Discussion guide? • What are reasons for not using this guide, or suggestions for changes of this guide? • What is the knowledge of healthcare professionals about the key points of content: - Hepatic effects - Pregnancy and lactation - Hematologic effects - Infections? • Are the patient cards delivered to patients? • What is the behaviour of healthcare professionals relating to liver enzyme monitoring and discussion of risks with patients?	
Country(-ies) of study	The survey will be conducted in two waves at 18 months and at 3 years after launch of Aubagio in at least 5 countries, including at least 2 of the most populated 5 EU countries, with adequate translations in local	
Anathan	languages.	
Author	Tbd	

MARKETING AUTHORIZATION HOLDER(S)

Marketing	Sanofi-Aventis Group
authorization holder(s)	[name]
	[name]
MAH contact person	[name]

1 LIST OF ABBREVIATIONS

AE Adverse Event

EMA European Medicines Agency

EU European Union

HCP Healthcare Professional

MAH Marketing Authorization Holder

MG Medication Guide

MS Multiple Sclerosis

PC Patient Card

PIL Patient Information Leaflet

RMP Risk Management Plan

SAE Serious Adverse Events

SmPC Summary of Product Characteristics

2 RESPONSIBLE PARTIES

Ipsos, together with Sanofi Genzyme, will be involved in the preparation of the protocol and its amendments and will develop the survey and analyse the results.

Ipsos will also be involved with the recruitment of healthcare professionals (HCPs) and management of the questionnaire.

The survey is sponsored by the global medical affairs department of Sanofi Genzyme.

3 SYNOPSIS

Title

Behaviour and Knowledge Survey regarding the educational materials provided to the HCP population prescribing Aubagio (cross-sectional survey).

Rationale and background

The efficacy of Aubagio was demonstrated in two placebo controlled phase III studies, the TEMSO and the TOWER study, that evaluated once daily doses of teriflunomide 7mg and 14mg in patients with multiple sclerosis (MS). To date, only the 14mg dose has been approved by European Medicines Agency (EMA). However, serious adverse events (SAEs) relating to liver function, susceptibility to infection and potential teratogenicity mean that implementation of Risk Management Plan (RMP) educational materials has been agreed between Marketing Authorization Holder (MAH) and EMA. The healthcare professional (HCP) educational pack consists of the Summary of Product Characteristics (SmPC) and "Healthcare Professional Education/Discussion Guide". The core elements of the HCP educational materials is the "Healthcare Professional Education/Discussion Guide". These are aimed at ensuring early detection of key symptoms indicative of adverse events (AEs), communication of risks of symptoms and the importance of periodic monitoring, and to inform about benefit-risk decisions before each treatment course.

The risk management knowledge and behaviour of HCPs prescribing Aubagio will provide assessment of the effectiveness of the RMP educational materials in HCPs. Very little published research exists relating to the evaluation of RMP educational materials, however, the methods of extant published literature have been used to guide proposals wherever possible.

Research question and objectives

The objective of the survey is to assess descriptively knowledge and behaviour of HCPs who prescribe Aubagio about the key items of the educational materials and thus the effectiveness of these materials to promote the safe and adequate use of Aubagio. Research questions relate to the extent of the HCP's understanding and awareness of the risks associated with use of the product, the key safety messages in the content of the "Healthcare Professional Education/Discussion Guide" and knowledge of risk minimisation activities to be undertaken.

Study design

The survey will be conducted in two waves at 18 months and at 3 years after launch of Aubagio in at least 5 countries, including at least 2 of the most populated 5 European Union (EU) countries. The surveys will be conducted online, using a structured questionnaire. Results will be analysed and reported to the EMA.

Population

The population for this study will be a sample of HCPs involved in the treatment of MS using Aubagio. To have wide coverage of HCPs across the EU, the survey will be conducted in at least 5 countries of the EU. Based on an estimation of Aubagio prescribers across Europe, the survey will be administered to approximately 200 HCPs.

Variables

The following elements will be collected and assessed at each wave:

- Knowledge of the HCP Education/Discussion guide
- 2. Use of HCP Education/Discussion guide, and suggestions for change of the guide
- 3. Knowledge of the key points of the content:
 - a. Hepatic effects and associated assessment of liver enzymes
 - b. Pregnancy and lactation. It includes pregnancy check, contraception information and implementation, and knowledge on the accelerated elimination procedure of teriflunomide from the blood, and existence of the Pregnancy Registry.
 - c. Hematological effects
 - d. Infections
- 4. Behaviour relating to liver enzyme monitoring and discussion of risks with patients (including delivery of Patient Card (PC) to patients).

Data sources

Data regarding the known distribution of neurologists and MS sub-specialists for participating countries will be supplied by the MAH. All other data will be collected via HCP self-report in a questionnaire.

Study size

The survey will be administered to 200 HCPs.

Data analysis

Descriptive analyses only will be performed. Sub-populations will be analyzed to identify patient groups that may require further education efforts. A threshold of 70% will be defined as 'adequate' knowledge. There is no pre-defined threshold for behavior.

Milestones

The survey will be conducted in 2 waves at 18 months and at 3 years after launch of Aubagio in at least 5 countries, including launch in at least 2 of the most populated 5 EU countries.

4 AMENDMENTS AND UPDATES

Number	Date	Section of study protocol	Amendment or update	Reason
1	Febr. 27, 2017	All	New format	New format
2	Date	Text	Text	Text
	Date	Text	Text	Text

5 MILESTONES

Milestone	Planned date	
Start of data collection Wave 1	March 2016	
End of data collection Wave 1	May 2016	
Interim report 1	November 2016	
Start of data collection Wave 2	June 2017	
End of data collection Wave 2	End of September 2017	
Final report of study results	December 2017	

6 RATIONALE AND BACKGROUND

BACKGROUND

Safety hazards

Not applicable – this is an online survey evaluating the effectiveness of minimisation measures of a RMP.

Safety profile

For the safety profile of Aubagio, please refer to the SmPC.

Description of Aubagio Risk Management Plan

The Aubagio RMP includes risk minimisation measures to support the safe use of the product. Educational materials form the core element of risk minimisation.

The primary objectives of the educational materials are to:

- Ensure early detection of symptoms indicative of AEs
- Communicate risks of symptoms, and the importance of periodic monitoring, to patients and prescribers
- Inform about benefit-risk decisions before each treatment course.

HCPs will receive relevant educational materials in hard copy for their own use. The HCP educational pack consists of the "Healthcare Professional Education/Discussion Guide" and the "Summary of Product Characteristics (SmPC)".

Additionally, the educational materials will be available on a MS One to One website to provide electronic access to HCPs who prescribe the product.

Relevant published research

This study will assess the knowledge and behaviour of HCPs who prescribe Aubagio about the items of the educational materials and thus the effectiveness of these materials to promote the safe and adequate use of Aubagio.

Alongside two other surveys ("A Tracking Survey Assessing the Distribution of Hard Copy and Online Risk Minimisation Materials relating to Aubagio" and "A Cross-Sectional Survey assessing the Effectiveness of minimisation measures of a Risk Management Plan (RMP): Behaviour and Knowledge Survey in patients treated with Aubagio") this is the first study to assess the effectiveness of the Aubagio RMP educational materials. Historically, there have been few published studies reporting the effectiveness of risk management interventions¹. This still remains the case, which may be due to the relative recent enforcement of assessing effectiveness of RMP measures.

RATIONALE

This RMP assessment of effectiveness survey will provide information relating to HCPs' understanding of the risk messages that are discussed in the "Healthcare Professional Education/Discussion Guide" for Aubagio prescribed for MS. It will evaluate both the knowledge and behaviour of HCPs that are prescribing Aubagio. There are limited published studies reporting HCPs' knowledge of tools used in risk management plans. The findings of this study may make an important contribution to the literature as well as providing the first data regarding knowledge and behaviour relating to risk minimisation with Aubagio specifically.

7 RESEARCH QUESTION AND OBJECTIVES

Research questions:

- 1. What is the knowledge of HCPs about the HCP Education/Discussion Guide?
- 2. Do HCPs use the HCP Education/Discussion Guide and are there suggestions for change of the guide?
- 3. What is the knowledge of HCPs of the key points of the content
 - a. Hepatic effects and associated assessment of liver enzymes
 - Pregnancy and lactation. It includes pregnancy check, contraception information and implementation, and knowledge on the accelerated elimination procedure of Aubagio from the blood, and existence of the Pregnancy Registry
 - c. Hematological effects
 - d. Infections.
- 4. What is the behaviour of HCPs relating to liver enzyme monitoring and discussion of risks with patients (including delivery of PC to patients)?

7.1 PRIMARY OBJECTIVE

The objective of the study is to assess descriptively knowledge and behaviour of HCPs who prescribe Aubagio about the items of the educational materials and thus the effectiveness of these materials to promote the safe and adequate use of Aubagio.

7.2 SECONDARY OBJECTIVES

Not applicable.

8 RESEARCH METHODS

8.1 STUDY DESIGN

In this international, cross-sectional study, information will be collected regarding the knowledge and behaviour relating to risk minimisation (as described in the HCP Education/Discussion Guide) of HCPs involved in the treatment of MS using Aubagio.

This is not an interventional study to evaluate the impact of a predefined therapy or procedure.

Data will be collected in two distinct waves (Wave 1 and Wave 2). The survey will be conducted online using structured questionnaires, comprising of questions where the response format is either the selection of a single response or selection of a number of responses as appropriate. Results will be analysed and reported to the EMA.

8.2 SETTING

The survey is conducted in 2 waves at 18 months and at 3 years after launch of Aubagio in at least 5 countries, including launch in at least 2 of the most populated 5 EU countries. Collection of survey data will take place online.

8.2.1 Duration of the study

Start of data collection for Wave 1 is at 18 months after launch in 2 of the most populated EU countries (Feb. 2016).

End of data collection for Wave 2 is (September 2017).

8.2.2 Eligibility criteria

8.2.2.1 Inclusion criteria

- HCP is a neurologist/MS specialist
- HCP has already prescribed Aubagio at study entry
- HCP supplies informed consent by ticking a box on the survey website.

8.2.2.2 Exclusion criteria

- HCP has not prescribed Aubagio
- For Wave 2 only: participation in the questionnaire in Wave 1.

8.2.3 Analysis populations

All surveys returned with at least one response completed will be analysed.

8.2.4 Modalities of recruitment

8.2.4.1 Physician selection

The survey is conducted in at least 5 countries of the EU. HCPs involved in the treatment of MS patients receiving Aubagio will be invited to take part.

For the selection of HCPs free found recruitment will be used. Multiple approaches will be used and will include:

- Recruitment via online panels panels exist for HCPs and will be used as the first recruitment approach
- Telephone recruitment hospital/center contact information will be used in order to identify appropriate HCPs for the study
- Snowballing we will ask respondents to suggest other potential respondents that may be interested in participating.

The registered HCP population will be described in terms of date when qualified as a doctor and MS specialist, practice setting and patient caseload and compared in each participating country with the known distribution of neurologists and MS sub-specialists to ensure representativeness.

HCPs will provide informed consent and data will be anonymous for the MAH.

8.2.4.2 Patient selection

Not applicable.

8.3 VARIABLES

Knowledge is defined as awareness and understanding of important risk minimisation information contained in the HCP Education/Discussion Guide. Important risk information measured:

- Awareness and use of the HCP Education/Discussion Guide
- Identification of symptoms indicating AEs associated with the liver, hematological effects, and infection
- Awareness of the accelerated elimination procedure of Aubagio from the blood
- Awareness of the need for contraception while taking Aubagio
- Awareness of the existence of the Pregnancy Registry.

Behaviour is defined as report of appropriate risk minimisation behaviour. Appropriate risk minimisation behaviour measured:

Using the HCP Education/Discussion guide

- Undertaking liver function monitoring as per SmPC
- Discussion of risks with patients
- Delivery of PC to patients.

Both knowledge and behaviour will be measured via self-report using a questionnaire which HCPs will complete. To a high response rate a more personal approach may also be used (e.g. via mail or interview). The questionnaire will measure knowledge and behaviour using questions with single choice or multiple choice responses (as appropriate). The questionnaire has been user tested by HCPs (described below).

Potential confounding factors

- 1. Some HCPs may only have small numbers of patients eligible to be prescribed Aubagio. Approximate number of patients treated with Aubagio will be recorded and included as a variable for sub-group analysis.
- 2. Length of time since last prescription of Aubagio to a patient will be recorded and included as a variable for sub-group analysis.

8.4 **DATA SOURCES**

Data regarding the known distribution of neurologists and MS specialists for participating countries will be supplied by the MAH. All other data will be collected via HCP self-report in the online questionnaire.

The online questionnaire has been developed by psychologists with experience of developing questionnaires ([name], [name]). It has been tested by HCPs who would be eligible to prescribe Aubagio.

User testing

Twelve HCPs (4 in the UK, 4 in Germany, 4 in Spain) participated in recorded interviews. During the interviews, the HCPs completed the questionnaire aloud and gave feedback on its clarity/ acceptability. Transcribed interviews were subjected to a content analysis and the findings used to refine the questionnaire. Modifications included clarification of some terms and alterations to the response format of some items.

8.5 STUDY SIZE

8.5.1 Determination of sample size

Based on an estimation of Aubagio prescribers across Europe, the survey will be administered to approximately 200 HCPs.

8.5.2. Sample size

It is planned to recruit 200 HCPs.

8.6 DATA MANAGEMENT

8.6.1 Data collection schedule

HCP data

Data will be collected online at 18 months and 3 years after launch of Aubagio in the participant countries.

Physicians who were recruited via methods as described previously will be sent an invitation email. The email will contain a link to the online study questionnaire and an email address to contact the research team if further information about the study is required. The invitation email and questionnaire will be translated into the local languages of participating countries.

On following the link within the invitation email, the information sheet will be displayed. HCPs will also be provided with an email address to make contact with the research team in the event of having questions prior to consent into the study. The information sheet and consent statement will emphasize that answers are anonymous and confidential. Following receipt of consent, the HCP will be able to move into the pages of the online questionnaire. In order to minimize missing data, it will be mandatory to answer all questions within the questionnaire.

The first elements of the questionnaire will relate to the eligibility criteria. If any of the answers indicate that the HCP is ineligible (e.g. has not prescribed a single dose of Aubagio), they will be taken to a page thanking them for their participation and explaining that they are not eligible to take part.

Following completion of the questionnaire the HCP will be taken to a page thanking them for their participation.

All survey tools (the text of the invitation email, information sheet, consent wording and questionnaire items) are available in Appendix 1.

HCP population data

In order to provide information regarding the representativeness of the HCPs completing the questionnaires as regards to the overall population of physicians prescribing Aubagio, known MS population statistics for participating countries will be supplied by the MAH.

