8.7 DATA ANALYSIS

8.7.1 Primary analysis

Descriptive analyses only (e.g. frequency distributions for each item) will be performed on the overall population of participating prescribers.

The response on knowledge is considered satisfactory if participants provide >70% correct answers. There is no pre-defined threshold for the behavior.

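### The protocol text gives no way to tell recalled from looked-up answers, so the knowledge result judged against >70% may be biased upward by an unknown amount

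*Protocol*

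**What the plan says.** Section 8.1 sets the mode: "The survey will be conducted online using structured questionnaires". Section 8.6.1 describes the route, an invitation e-mail of which it says: "The email will contain a link to the online study questionnaire". It also makes every question mandatory. Section 8.3 allows mail or interview as well, but only in connection with the response rate.

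On access to the materials, section 6 states that "HCPs will receive relevant educational materials in hard copy for their own use" and that "the educational materials will be available on a MS One to One website to provide electronic access to HCPs who prescribe the product".

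Section 8.3 ties the outcome to the same document: "Knowledge is defined as awareness and understanding of important risk minimisation information contained in the HCP Education/Discussion Guide". Section 8.7.1 then gives the only numerical criterion: "The response on knowledge is considered satisfactory if participants provide >70% correct answers". Behaviour has no threshold. Under 8.7.2, more detailed analysis is considered only where the result is below 70%.

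Section 8.9 concedes that self-reported information cannot be verified, with work setting as its example. It does not mention look-ups. The survey tools are listed as Appendix 1 documents, kept separately from the protocol.

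**The concern.** The document that defines the correct answers is planned to be within reach of people who mostly answer on their own. With every item mandatory, a respondent who is unsure cannot skip, which plausibly adds to the temptation to check.

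A successful look-up can only raise the score. The score then partly measures access to the Guide during the survey, whereas the objective in 7.1 is to judge whether the materials promote safe and adequate use. Because further analysis is considered only below 70%, an inflated result could also switch off the protocol's own follow-up of weak areas. A larger sample does not reduce a bias of this kind.

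**Working it through.** **What the protocol text offers to separate the two kinds of answer**

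| Section | Content on look-ups |
|---|---|
| 8.3 Variables | None |
| 8.6.1 Data collection schedule | No supervision, time limit or request for unaided answers described |
| 8.6.2 Data collected | No item listed; the list is not exhaustive, since it omits patient numbers and time since last prescription, which 8.3 says are recorded |
| 8.7.1, 8.7.2 Analyses | None |
| 8.8.1 Quality control | States that source data cannot be verified |
| 8.9 Limitations | Self-report unverifiable; look-ups not named |

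**Inputs for an illustration**
- From the protocol: the 70% criterion (8.7.1) and 200 HCPs (8.5.2: "It is planned to recruit 200 HCPs"). Section 8.5.1 bases the 200 on an estimate of prescriber numbers, so there is no statistical derivation to reproduce.
- Assumed, not in the documents: closed-book correct rate k, correct rate c among those who look up, and look-up share u. The calculation also assumes that the criterion applies to the mean share of correct answers.

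**Share of look-ups at which the observed result reaches 70%**

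Observed = (1 - u)k + uc. Setting this to 0.70 gives u = (0.70 - k)/(c - k).

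| k | c = 90% | c = 95% | c = 100% |
|---|---|---|---|
| 65% | 0.05/0.25 = 20% | 0.05/0.30 = 17% | 0.05/0.35 = 14% |
| 60% | 0.10/0.30 = 33% | 0.10/0.35 = 29% | 0.10/0.40 = 25% |

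The range is 14% to 33%. For lower true knowledge the share is larger: at k = 50% it is 0.20/0.50 = 40% with c = 100%, and 0.20/0.40 = 50% with c = 90%.

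**Comparison with sampling error**

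This takes 200 respondents in the wave judged; the protocol does not say whether 200 is per wave.
- 95% half-width at 70%: 1.96 × √(0.70 × 0.30/200) = 0.0635, about 6.4 points.
- Bias = u(c - k). With k = 60% and c = 90% it is 0.20 × 0.30 = 6 points at u = 20%, and 0.50 × 0.30 = 15 points at u = 50%.
- For a single item with the same k and c, the binomial probability of at least 141 of 200 correct (more than 70%) is 0.1% with no look-ups, 10% at u = 20%, 35% at u = 30% and 94% at u = 50%.

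Under these assumptions, a bias from moderate look-up is about as large as sampling error or larger.

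**The case against.** **The safeguards may exist in documents not shown.** An instruction to answer from memory, or an item on consulting materials, would naturally sit in the information sheet or questionnaire. This stands. A reader might infer that nothing is planned to detect look-ups; the documents do not support that, and the point is limited to the protocol text. An instruction alone would still not measure compliance, and an analysis plan cannot use a variable that was never collected.

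**Possession of the Guide is planned, not shown.** Section 6 describes intended distribution, awareness and use of the Guide are survey outcomes, and distribution has its own tracking survey. This stands too. Interview is also possible, so not every response need be self-completed, although mail is just as open-book.

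**Consulting the Guide is good practice.** Section 8.3 counts using the Guide as appropriate behaviour. But the protocol treats behaviour and knowledge as separate constructs, and a looked-up answer blurs them. Some knowledge items, such as awareness of the Guide itself, are hardly affected.

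**The criterion is only a descriptive benchmark, and its reading is open.** There is no test, and item frequencies are reported as well. The wording of 8.7.1 can also be read per participant, and the mean-score mixture above does not apply to that reading. Both stand as limits on the illustration.

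**Why not judge >70% on the unaided respondents alone?** That is tempting but not justified. It would select on a self-declared choice, remove HCPs who consult the Guide, keep those who do so without saying, and break comparability with Wave 1.

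**Conclusion.** The point holds as a design weakness and an unnamed limitation. It is not a contradiction or an arithmetic error. As far as the protocol text shows, nothing distinguishes recalled from looked-up answers before the >70% criterion is applied, and any bias from successful look-ups is upward.

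Its size cannot be derived from the documents. The 14-33% range rests on assumed true knowledge of 60-65%, assumed look-up scores of 90-100% and a mean-score reading of 8.7.1. It shows that a misleading pass is possible when true knowledge lies a little below the threshold. A reader might go further and infer that the survey will declare knowledge satisfactory when it is not; without a look-up rate or a closed-book score, the documents do not support that. What changes is how much a result above 70% can be taken to show. This is a worthwhile, inexpensive improvement, and it does not invalidate the survey.

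**What to change.** For Wave 2 only, since Wave 1 collection was planned for March to May 2016 and this version is dated 8 May 2017, shortly before the planned June 2017 start:

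- **8.6.2:** unless the questionnaire already has it, add one item at the very end, after all knowledge items, asking whether the Guide, SmPC or website was consulted while answering. Record completion time if the system allows.
- **8.7:** keep the >70% judgement on all respondents. Add a supplementary table of the knowledge result without those who report consulting materials, and state whether the >70% conclusion holds in both.
- **8.9:** state that unaided recall cannot be verified and that look-ups would bias measured knowledge upward.

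Blocking return to earlier pages is not worth adding, because it does not stop anyone opening a booklet or another website.

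The cost is one extra item to translate for at least 5 countries, one more table and one sentence. The item has no counterpart in Wave 1, some look-ups will go unreported, and the supplementary table rests on a smaller, self-selected group, so it should be read as a sensitivity check.
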